### 12.4 Statistical Analysis Plan

Note: Analyses will be performed separately for patients treated with mTOR inhibitors and patients with esophagus radiation.

For the primary objective, we will use the Wilcoxon rank sum test to compare the ordered categories of mucositis/esophagitis severity between treatment arms. A patient must complete at least 60% of the planned doses of placebo or glutamine to be considered evaluable in the statistical analysis. As a sensitivity analysis for the appropriateness of 60% dosing cut-off, we will analyze the outcome according to the proportion of drug taken. The proportional of drug taken will be computed as the ratio of number of doses taken to the total number of doses prescribed. For the mTOR inhibitor group, the denominator will reflect the total time that each patient is on the study. For the esophagus radiation group, the denominator will reflect the total number of doses that are prescribed during the delivery of radiation.

For the secondary objectives/endpoints, we will compare between treatment arms (1) the trajectories of the mucositis/esophagitis scores over time using linear mixed effects; (2) the proportion of patients developing mucositis/esophagitis using a Pearson chi-squared test; (3) the proportion of patients developing grade 3 or higher mucositis/esophagitis using a Pearson chi-squared test; (4) the duration of mucositis/esophagitis using the Wilcoxon rank sum test; (5) the time to develop mucositis/esophagitis using Kaplan-Meier estimates and the log rank test (due to right censoring in patients not developing mucositis/esophagitis); (6) the proportion of patients having treatment interruptions using a Pearson chi-squared test; (7) the

weight change using the Wilcoxon rank sum test; and (8) the QOL survey scores using the Wilcoxon rank sum test.

For the secondary objective of describing the toxicity profile, descriptive statistics will be provided on the grade and type of toxicity by treatment arm.

For the secondary objective of assessing the muscle breakdown in the esophagus radiation group, we will compare the muscle breakdown between the patients that received glutamine versus placebo. Muscle breakdown will be assessed by reviewing patient CTs pre-treatment, during weeks of radiation, 1 month post treatment, and 6 months post treatment. The CT image at the level of the third lumbar vertebra will be auto-segmented using Pinnacle software. One cross section will highlight the skeletal muscle mass while the other cross section will highlight the adipose tissue surrounding the vertebra. LBM (lean body mass) and FM (fat mass) will be estimated from skeletal muscle and adipose cross-sectional area (cm^2) at the third lumbar vertebra using the formulae described by Chamchod et al.

 $LBM_{CT}$  (kg) = 0.3 x [skeletal muscle at L3 (cm^2)] + 6.06

 $FM_{CT}$  (kg) = 0.042 x [total adipose tissue at L3 (cm^2)] +11.2

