# 10.1 Serious Adverse Event (SAE) Reporting

### Adverse Event Definition

The CTEP active version of NCI Toxicity Criteria may be used by the Investigator as a guide in determining the severity of adverse events.

Clinically significant adverse events (AEs) and Serious Adverse Events (SAEs) occurring during the study that are thought to be related to Glutamine or Best Supportive Care should be documented in the medical record.

Toxicities of all grades that are felt to be related to Glutamine or Best Supportive Care, and all grades of mucositis, esophagitis, and weight loss will be documented in the patient electronic medical record. Unless otherwise documented in the electronic medical record as clinically significant and study drug related, all lab abnormalities will be assumed to be related to the patient's other co-morbid conditions, prior therapies, other concomitant therapies/medications, or underlying cancer. In this study, only adverse events related to the study drug, not related to mTOR inhibitor therapy or radiation therapy will be recorded.

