# Secondary Endpoints

- For mTOR inhibitor patients, oral mucositis grade will be assessed at the following times: baseline, weekly during Cycle 1, and Day 1 of Cycle 2 and beyond, and end of study. For esophagus radiation patients, esophagitis grade will be assessed at the following times: baseline, weekly during radiation, end of treatment (or final week of radiation treatment based on number of weeks of radiation), and 1 month and 6 months post radiation therapy.
- For mTOR inhibitor patients, QOL will be assessed by MDASI-HN at the following times: baseline, Day 15 of Cycle 1, Day 1 of Cycles 2 and beyond, end of study, and 3 months and 6 months post end of treatment. For esophagus radiation patients, QOL will be assessed by MDASI-HN at the following times: baseline, Weeks 3, 5, and 7 of radiation, end of treatment (or final week of radiation treatment based on number of weeks of radiation), 1 month, 3 months, and 6 months post radiation therapy. For mTOR inhibitor patients, Patient Satisfaction with Study Medication will be assessed at Day 1 of Cycles 2 and beyond. For esophagus radiation patients, Patient Satisfaction with Study Medication will be assessed at Weeks 3, 5, and 7, end of treatment (or final week of radiation treatment based on number of weeks of radiation treatment based on number set as a Day 1 of Cycles 2 and beyond. For esophagus radiation patients, Patient Satisfaction with Study Medication will be assessed at Weeks 3, 5, and 7, end of treatment (or final week of radiation treatment based on number of weeks of radiation), and 1 month post radiation therapy.
- For mTOR inhibitor patients, body weight will be assessed at the following times baseline, weekly during Cycle 1, and Day 1 of Cycle 2 and beyond, and end of study. For esophagus radiation patients, body weight will be assessed at the following times: baseline, weekly during radiation, 1 month and 6 months post radiation therapy.
- For esophagus radiation patients, muscle breakdown will be assessed at baseline, weekly during radiation, 1 month and 6 months post radiation therapy.

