## 12.3 Sample Size

There will be a total of 180 patients in this study. The cohort of patients on mTORbased regimens will be 100, and the cohort of patients on radiation regimen will be 80.

For esophagus radiation, published data indicate that the distribution of patients by esophagitis grade is 0-1: 26%, 2: 37%, 3: 37% for patients not given glutamine. If we target a modest treatment effect (0-1: 50%, 2: 38%, 3: 12%) then 40 patients per treatment arm would give us 81% power (assuming a two-sided 5% alpha and use of the Wilcoxon rank sum test for analysis).

For mTOR inhibitor patients, we have unpublished data from 87 patients indicating that the distribution of patients by oral mucositis grade is 0-1: 69%, 2: 22%, 3: 9% for patients not given glutamine. If we target (0-1: 95%, 2: 5%, 3: 0%) as the results in the glutamine arm, then 50 patients per arm would give us 94% power (assuming a two-sided 5% alpha, and use of the Wilcoxon rank sum test for analysis).

These calculations were made using nQuery Advisor 7.0.

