### 12.5 Randomization and Blinding

Patients will be equally randomized between treatment arms using permuted blocks within strata separately for the two groups of patients. For patients who will receive mTOR inhibitor based therapy, randomization will be stratified by: prior mucositis (Y/N), and prior radiation therapy to the head and neck (Y/N). For patients who will

receive radiation to the esophagus, randomization will be stratified based on the volume of esophagus receiving 40 Gy: (1) 20-40%; (2) 41-60%; (3) 61-80%.

CORe will set up a Randomization website and the Investigational Pharmacy personnel will perform the randomization assignment.

Both patients and the research staff conducting the assessment will be blinded to the treatment assignment. Placebo powder identical to glutamine powder in appearance and taste will be compounded by Healios Nutrition Oncology, and both will be dispensed by Investigational Pharmacy at MD Anderson. At the end of the blinded phase, we will assess blinding by asking patients which study arm they believe they have been randomized to.

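### The primary test admits only patients who took at least 60% of doses, and no comparison of all randomised patients by assigned arm is planned

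*Combined protocol and SAP*

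**What the plan says.** Section 12.4 compares ordered severity grades between arms with the Wilcoxon rank sum test, separately in each cohort. The next sentence sets the analysis population: "A patient must complete at least 60% of the planned doses of placebo or glutamine to be considered evaluable in the statistical analysis". One sensitivity analysis is offered to examine the cut-off: "we will analyze the outcome according to the proportion of drug taken". How it would be done is not stated.

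The adherence ratio has a different denominator in each cohort. In the mTOR cohort it follows each patient's time on study. In the radiation cohort "the denominator will reflect the total number of doses that are prescribed during the delivery of radiation".

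Section 12.3 states that 40 "patients per treatment arm would give us 81% power" in the radiation cohort, and that 50 per arm give 94% in the mTOR cohort. Planned enrolment is 80 and 100, which is exactly 2 × 40 and 2 × 50.

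**The concern.** Excluding patients for doses not taken is a selection made after randomisation, and here it may depend on the outcome. The powder is swallowed (section 3.2), and grade 3 is partly defined by impaired intake or swallowing (section 9.0). In the radiation cohort, doses are counted during radiation and the endpoint is the worst grade by week six (section 12.2), so the two windows overlap. A patient whose esophagitis stops the powder could leave the set in which esophagitis is measured. That severity lowers adherence is an inference; the documents contain no data on it.

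Two consequences follow if it is true. If glutamine works, placebo has more high grades, more placebo patients are excluded, and the observed difference shrinks. If patients at the same grade adhere differently by arm, the test can favour either arm when there is no effect. The dose-proportion analysis conditions on the same post-randomisation variable and, as written, is not a comparison by assigned arm.

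Section 12.3 also makes no allowance for the patients that section 12.4 excludes.

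**Working it through.** **Inputs.** From section 12.3, with grades in the order 0-1 / 2 / 3:
- Radiation: control 26/37/37%, target 50/38/12%, 40 per arm.
- mTOR: control 69/22/9%, target 95/5/0%, 50 per arm.
- Two-sided 5%, Wilcoxon rank sum test.

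All adherence rates below are assumptions.

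**Step 1: the plan's own power.** Let p = P(control grade higher) + ½P(tie).
- Radiation: 0.37×0.50 + 0.37×0.88 + ½(0.26×0.50 + 0.37×0.38 + 0.37×0.12) = 0.5106 + 0.1575 = 0.6681.
- mTOR: 0.22×0.95 + 0.09×1 + ½(0.69×0.95 + 0.22×0.05) = 0.2990 + 0.33325 = 0.63225.

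Power = Φ((p − 0.5 − 1.96·SE0)/SE1). SE0 = √((1 − Σq³)/(6n)), where q is the pooled distribution, and SE1 is the standard error of p under the alternative.
- Radiation: SE0 = √(0.8777/240) = 0.0605 and SE1 = 0.0562, giving 81.1% (stated 81%).
- mTOR: SE0 = √(0.4461/300) = 0.0386 and SE1 = 0.0360, giving 94.2% (stated 94%).

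Both figures reproduce, but only with all 40 and all 50 per arm analysed. Simulating the tie-corrected test gives 81.0% and 96.1%, with null error of 4.9% and 5.0%. The steps below use simulation (1,000,000 trials per scenario; 400,000 for the random exclusions matched in size in step 2), so the mTOR baseline there is 96%.

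**Step 2: adherence falls with grade equally in both arms, and the target effect is true.** Share kept = Σ(grade probability × adherence). For radiation at 95/90/80%:
- Placebo: 0.26×0.95 + 0.37×0.90 + 0.37×0.80 = 0.876, so 12% are excluded.
- Glutamine: 0.50×0.95 + 0.38×0.90 + 0.12×0.80 = 0.913, so 9% are excluded.
- Grade 3 among those kept: 0.296/0.876 = 33.8% against 0.096/0.913 = 10.5%. The difference falls from 25 to 23 points.

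| Adherence by grade | Radiation excluded, placebo / glutamine | Radiation grade 3 difference | Radiation power | Same numbers lost at random | mTOR power | Same numbers lost at random |
|---|---|---|---|---|---|---|
| 95/90/80% | 12% / 9% | 23 points | 73.8% | 76.8% | 93.2% | 94.9% |
| 95/85/60% | 22% / 13% | 20 points | 64.5% | 73.0% | 89.3% | 94.7% |
| 95/85/50% | 25% / 14% | 18 points | 58.8% | 71.7% | 87.5% | 94.5% |

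With no true effect, two-sided error stays at 4.9-5.0%. Power falls by more than the lost numbers explain.

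**Step 3: adherence differs by arm at the same grade, with no true effect.** Placebo is held at 95/90/80%. With glutamine at 95/85/50% in the radiation cohort, grade 3 among those kept is 33.8% on placebo and 0.185/0.7465 = 24.8% on glutamine, although the true rate is 37% in both.

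| Glutamine adherence | Radiation two-sided error (part favouring glutamine) | mTOR two-sided error (part favouring glutamine) |
|---|---|---|
| 95/85/50% | 10.9% (10.5%) | 6.5% (5.5%) |
| 95/87/65% | 6.3% (5.2%) | 5.4% (3.8%) |
| 95/88/75% | 5.1% (3.2%) | 5.0% (3.0%) |

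The nominal part favouring glutamine is 2.5%. Swapping the arms mirrors these figures.

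**Step 4: what an all-randomised test could cost.** Suppose a share f of the glutamine arm is non-adherent and has control-arm grades. The glutamine distribution is then (1 − f)×target + f×control; for radiation at f = 0.1 it is 47.6/37.9/14.5%. The comparison is with analysing only adherent patients when exclusion is random.

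| Non-adherent | Radiation, all randomised | Radiation, random exclusion | mTOR, all randomised | mTOR, random exclusion |
|---|---|---|---|---|
| 10% | 71.8% | 76.9% | 88.3% | 94.1% |
| 20% | 61.0% | 71.8% | 76.3% | 91.3% |
| 30% | 49.5% | 65.7% | 61.6% | 87.4% |

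**The case against.** The strongest reply is that no bias has been shown. Section 12.5 provides for blinding and a matched placebo ("Placebo powder identical to glutamine powder in appearance and taste"), which favours equal adherence at a given grade. In that case type I error holds, and the restriction works against glutamine. The 10.9% needs a 30-point gap at grade 3, and the mildest unequal case barely moves two-sided error. This stands: the defect is a missing safeguard, and the error figures are illustrations.

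The denominators also limit exclusion. With dosing seven days a week from day 1 (assumed), 60% of a 5-, 6- or 7-week course is reached at about day 21, 25 or 29 (0.6 × 35, 42 or 49). A patient who stops after that stays evaluable, so losing 40-50% of grade 3 patients needs early stopping or long partial dosing. In section 9.0, starting narcotics also counts as grade 3 esophagitis, which need not mean inability to swallow. The harsher rates are therefore less plausible, though no onset times are given that would rule them out.

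In the mTOR cohort, a patient removed under section 8.0 for refusing the powder may remain evaluable because the denominator is time on study. Exclusion is then rarer than modelled, but grading is cut short, which is another gap in the same endpoint. The mTOR power figures also depend on the method by 2 to 4 points.

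The dose-proportion analysis may include patients below 60%. As it is unspecified, it cannot be relied on to fill the gap. Dilution is a real cost of the all-randomised test, but it affects power, not validity.

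**Conclusion.** The concern holds. As written, the only confirmatory test in each cohort is run on a set chosen by post-randomisation behaviour, and the plan supplies no comparison that randomisation protects. This follows from the text and needs no adherence assumption.

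The size of the effect is unknown. Under equal grade-dependent adherence, type I error is intact, and power falls to 74-59% in radiation and 93-87% in mTOR. Under unequal adherence with no effect, error is 5.1-10.9% and 5.0-6.5%. An all-randomised test is valid in both situations, as far as grades are complete. Whether it has more or less power than the restricted test depends on why patients stop: it keeps 81% in radiation if non-adherence follows grade and the section 12.3 targets hold for everyone randomised, and it loses power if non-adherent patients forgo the benefit. The case for the change is validity.

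**What to change.** - **Section 12.4.** Make the primary Wilcoxon test a comparison of all randomised patients by assigned arm. Keep the 60% set and the dose-proportion analysis as sensitivity analyses, and specify the latter.
- **Grade collection.** State that scheduled grades continue to be collected after the study powder stops, including after removal from study treatment, unless consent is withdrawn. Report missing grades by arm. Section 12.2 already schedules these assessments ("For esophagus radiation patients, esophagitis grade will be assessed at the following times"; "For mTOR inhibitor patients, oral mucositis grade will be assessed at the following times").
- **Database.** Section 10.1 has all mucositis and esophagitis grades documented in the medical record, but also says "only adverse events related to the study drug, not related to mTOR inhibitor therapy or radiation therapy will be recorded", and section 10.2 limits adverse events in the study database in the same way. Name the endpoint grades as entered in the study database regardless of attribution.
- **Section 12.3.** State that 81% and 94% assume all 40 and all 50 per arm are analysed and that the target distributions apply to everyone randomised. If the sponsor expects the targets only in adherent patients, restate the power with a stated non-adherence rate, as in step 4.

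The cost is text, plus database entry of grades already being collected. No change in enrolment is proposed. The trade-off to accept openly is possible dilution: about 72/61/50% power in radiation and 88/76/62% in mTOR at an assumed 10/20/30% non-adherence.

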### 1.2 Secondary Objectives:

- To assess whether glutamine regimen improves quality of life (QOL) in patients during mTOR inhibitor containing regimen and esophagitis during radiation to esophagus.
- To assess whether glutamine improves other measures of mucositis/esophagitis including incidence of any mucositis/esophagitis, incidence of grade 3 or higher mucositis/esophagitis, duration of mucositis/esophagitis, delay in onset of mucositis/esophagitis, and interruption of cancer treatment due to mucositis/esophagitis.
- To assess whether glutamine affects weight loss after six months of treatment for mTOR inhibitor patients and after completion of radiation therapy for esophagus radiation patients.
- To assess toxicity profile of glutamine.
- To assess whether glutamine affects muscle breakdown.

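### The QOL comparison has no stated use of the baseline score or repeated visits, and a six-month weight comparison would drop mTOR patients who stop early

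*Combined protocol and SAP*

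**What the plan says.** Section 12.4 lists eight secondary comparisons between arms, run separately in the two cohorts. Item (1) compares "the trajectories of the mucositis/esophagitis scores over time using linear mixed effects". Item (7) compares the "weight change using the Wilcoxon rank sum test", and item (8) compares "the QOL survey scores using the Wilcoxon rank sum test". Items (7) and (8) name no visit, covariate or rule for missing values. Item (8) also names no MDASI-HN summary score and does not say whether the score is raw or a change from baseline.

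The data collected are much richer (section 12.2, Secondary Endpoints):

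- **QOL, mTOR cohort:** "QOL will be assessed by MDASI-HN at the following times: baseline, Day 15 of Cycle 1, Day 1 of Cycles 2 and beyond", then end of study and two later visits.
- **QOL, radiation cohort:** "baseline, Weeks 3, 5, and 7 of radiation, end of treatment", then 1, 3 and 6 months after radiation.
- **Weight, mTOR cohort:** "body weight will be assessed at the following times baseline, weekly during Cycle 1, and Day 1 of Cycle 2 and beyond", and at end of study.

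The weight objective in section 1.2 is "To assess whether glutamine affects weight loss after six months of treatment for mTOR inhibitor patients". For the radiation cohort the objective refers instead to completion of radiation.

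**The concern.** QOL is the first secondary objective. A two-sample rank test takes one value per patient. Applied to a single post-baseline score, it leaves between-patient differences that were present before treatment in the error term, and it discards every other visit. The plan already has a repeated-measures model for grade but does not extend it to QOL.

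Because no score or visit is named, the result also depends on a choice not yet made. The MDASI-HN has 22 items (13 core plus 9 head-and-neck, section 5.3.1), and the radiation cohort has seven post-baseline visits.

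For weight the issue is different. In the mTOR cohort, having a six-month value depends on staying on treatment, which is determined after randomisation. If early leavers lose more weight, or if glutamine changes who stays, a comparison limited to those with a six-month value no longer compares the randomised groups.

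**Working it through.** **The plan's own figures.** Section 12.3 gives power only for the primary endpoint: 81% with 40 per arm (radiation) and 94% with 50 per arm (mTOR). A tie-corrected normal approximation to the Wilcoxon test, with the stated grade distributions, gives 80.8% and 94.1%, so both reproduce. They do not depend on this point. For QOL and weight the documents give no effect size, SD, correlation, dropout rate or power, so everything below rests on assumed values shown as ranges.

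**Variance of the arm comparison.** Let r be the correlation between baseline and follow-up, with equal SDs, and set the variance for a single raw follow-up score to 1.

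- Raw score: 1
- Change score: 2(1 - r)
- Baseline-adjusted score: 1 - r²
- Adjusted relative to change: (1 - r²) / [2(1 - r)] = (1 + r)/2

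*QOL, if item (8) means raw scores.* At r = 0.5, 1 - 0.25 = 0.75, a 25% cut. At r = 0.7, 1 - 0.49 = 0.51, a 49% cut. These equal 1/0.75 = 1.33 and 1/0.51 = 1.96 times as many patients.

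*QOL, if item (8) means change scores.* At r = 0.5, (1 + 0.5)/2 = 0.75, a 25% cut. At r = 0.7, (1 + 0.7)/2 = 0.85, a 15% cut.

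*Weight, already a change.* At r = 0.9, (1 + 0.9)/2 = 0.95, a 5% cut.

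**What this means for power on QOL.** With an assumed effect of 0.5 SD and two-sided 5% alpha, power is approximately Φ(0.5·√(n/(2f)) - 1.96), where f is the variance factor and n the number per arm:

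| Analysis | f | n = 40 | n = 50 |
|---|---|---|---|
| Raw score | 1 | 61% | 71% |
| Change, r = 0.5 | 1.00 | 61% | 71% |
| Change, r = 0.7 | 0.60 | 82% | 90% |
| Adjusted, r = 0.5 | 0.75 | 73% | 82% |
| Adjusted, r = 0.7 | 0.51 | 88% | 94% |

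Using several visits adds more. If all visits correlate equally at 0.5, the baseline-adjusted mean of three visits has f = (1 + 2 × 0.5)/3 - 0.25 = 0.417.

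**Who has a six-month mTOR weight.**

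- Section 5.3.4 places end of study within four weeks of the last mTOR dose. Section 8.0 lists four weeks after that dose as a completion point.
- Section 6.1 marks a weight at the 6-month visit. Its footnote f confines that visit to patients still on mTOR therapy, whereas the column heading and footnote h place it after the end of treatment. Section 12.2 lists no mTOR weight after end of study.
- Take a patient who stops in month 2. Under footnote f there is no 6-month visit. Under footnote h the visit falls at about month 2 + 6 = 8. Neither gives a scheduled weight six months after starting, although weekly and per-cycle weights up to stopping exist.

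The share of such patients is not stated. If 20%, 40% or 60% of the mTOR cohort lack the value, 50 per arm becomes 40, 30 or 20. Power for 0.5 SD of the analysed outcome then falls from 71% to 61%, 49% or 35%. The size of any bias cannot be computed from the documents.

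**The case against.** The Wilcoxon test is valid and robust for a two-arm secondary comparison, and MDASI-HN items are bounded 0-10 ratings. The variance ratios above are normal-theory results for means and were not recomputed for skewed or tied scores. That stands, and the gains are approximate.

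The plan is silent about the QOL score; it does not exclude baseline. A reader might infer that baseline is certainly ignored, but the documents do not say so. Section 5.3.1 is headed as an assessment of improvement, so change scores are a fair reading, and a rank test could be run on a per-patient summary over visits. Against that, item (7) says change and item (8) does not. Either way adjustment gains precision at the assumed correlations, and the intended score has to be stated.

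Early leavers in the mTOR cohort do have an end-of-study weight, so some weight change exists for them, and section 12.4 never says that only patients with complete data are used. This also stands. But their last weight is not in general a six-month weight, and no rule brings it into a six-month comparison.

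A mixed model is not a cure. It relies on data being missing at random, and it implies a weight for patients who have died. Nor does it undo the requirement in section 12.4 that patients take 60% of planned doses to be evaluable. That rule sits in the primary-analysis paragraph but is worded generally, and it too selects after randomisation. Visit timing varies as well: radiation weeks and mTOR cycles differ between patients. These points shape the fix. None of them shows that an unadjusted rank test does as well for QOL.

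**Conclusion.** The point holds for QOL as a missing specification and an avoidable loss of precision. Adjustment cuts variance by 25-49% if raw single-visit scores are meant, or 15-25% if change scores are meant, at an assumed correlation of 0.5-0.7.

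For weight it holds only for the mTOR six-month comparison, where early leavers drop out of the analysis for want of a scheduled value. Two stronger readings are not supported:

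- That the weight test ignores baseline. The outcome is change, so baseline is already subtracted, and adjustment adds about 5% at an assumed correlation of 0.9.
- That the six-month selection affects both cohorts. The radiation objective refers to completion of radiation.

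Only secondary endpoints are involved. The change is worth making because it uses data already collected.

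**What to change.** Amend section 12.4 before unblinding:

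1. **QOL.** Name one MDASI-HN summary score (for example the mean of the 22 items). Analyse it with a mixed model for repeated measures containing arm, visit, arm-by-visit, baseline score and that cohort's randomisation strata from section 12.5. Name one contrast. Define time points so that they allow for varying radiation length and number of cycles, for example by indexing radiation visits to the end of radiation and fixing a common window for the mTOR cohort.
2. **mTOR weight.** Use the same type of model on all post-baseline weights, with the contrast at six months. State the missing-at-random assumption and how deaths are handled.
3. **Analysis set.** Apply the weight model, and preferably the QOL model, to all randomised patients with data, not only those meeting the 60% dose rule.
4. **Reconcile first.** Sections 6.1 (column heading, footnotes f and h) and 12.2 must agree on who has the mTOR 6-month visit, when it falls and whether weight is taken, before the six-month contrast is set.
5. **Sensitivity.** Keep the Wilcoxon tests, with the score and visit stated.

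The cost is SAP wording, modest programming and reliance on model assumptions for secondary endpoints. No new data are needed, and sample size and primary power do not change.
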